4.1 Investigational product(s)

The following investigational products will be used in the study:

Ciprofloxacin group

Active ciprofloxacin oral suspension 5% (5 g ciprofloxacin in 100 ml) for single dose only. Ciprofloxacin will be administered orally in suspension formulation in a dose of 20 mg/kg body weight only once (maximum dose will be 750 mg).

Erythromycin group

Two bottles of 100 ml (200 mg/5 ml) of active erythromycin suspension for doses 1 to 12. Erythromycin will be administered in a dose of 12.5 mg/kg body weight every 6 hours for 3 days (maximum individual dose of 500 mg; total 12 doses).

Ciprofloxacin is manufactured by Bayer AG, Germany. Erythromycin (Paediathrocin manufactured by Abbott) will be bought and provided by Bayer AG.

4.2 Supply, packaging, labelling and storage

The study drugs will be supplied as suspension in light protected, brown glass bottles.

The labelling of ciprofloxacin suspension and erythromycin suspension will be done by Bayer Leverkusen. Each box will be clearly labelled with the following information:

- “Study number”
- “Bulk Batch No.”
- “Dosage: 20 mg/kg, once only (ciprofloxacin)
or 12.5 mg/kg 6 hourly for 3 days (erythromycin)”
- “Random number”
- “Patients initials (to be completed by the investigator)”
- “Bottle no.”
- “Centre no.”
- “Store below 25°C”
- “For clinical trial use only”.

The drugs provided by Bayer AG will be used exclusively for the study as specified in the protocol. All drug supplies will be retained by the Research Officer working for the protocol in a safe and secure place at controlled room temperature of < 25°C and protected from light until use. The Research Officer will confirm receipt of the study drugs on the Drug Supply Confirmation Form, a copy of which will be returned to Bayer AG. The Research Officer will also be responsible for dispensing the study medication as specified. The study-ward nurse will be responsible for administering the drug to the patients. The Research Officer will also be responsible for maintaining drug inventory and accountability records. All unused material must be accounted for and returned to Bayer AG at the end of the study.

5. Investigational plan

5.1 Overall design and plan of trial

This is a randomised, open, parallel group clinical trial to compare the efficacy and safety of a single dose of ciprofloxacin oral suspension 20 mg/kg with a 3-day course of erythromycin oral suspension administered in a dose of 12.5 mg/kg every 6 hours (12 doses) in the treatment of children, aged 2 to 15 years, with clinically severe cholera due to *V. cholerae* O1 or O139.

The sample size of the study has been determined to include 80 valid patients in each of the two treatment groups, i.e. a total of 160 patients. It is estimated that approximately 180 children, fulfilling eligibility criteria, will be initially enrolled to ensure the desired sample size.

Eligible patients will be admitted to the Clinical Study Ward of the Dhaka and Matlab Hospitals of ICDDR,B. Upon admission, their weight (dehydrated weight) and vital signs will be recorded, and a thorough physical examination including assessment of dehydration (following WHO guidelines) will be made. Patients will then be rehydrated using intravenous Dhaka Solution (133, 13, 98 and 48 mmol/l of sodium, potassium, chloride and bicarbonate respectively) over 3-4 hours. Thereafter, they will be observed over a 4-hour Observation Period when their hydration will be maintained using the rice-based ORS (containing 3.5, 2.5, 1.5 and 50 gram/l of sodium chloride, sodium bicarbonate, potassium chloride and rice powder). Dhaka Solution, as used for initial rehydration, will be used for patients whose hydration cannot be maintained by rice-based ORS.

Patients who have a stool output of 20 ml/kg or more during the Observation Period, and who have *V. cholerae* demonstrated in dark-field microscopic examination of their stool sample, will be enrolled upon obtaining written informed consent of their parents or guardians. If possible, assent must be obtained from the child. Patients will then be randomly assigned to receive one of the two treatment regimens.

Children will be hospitalised for 5 days or until resolution of their diarrhoea whichever is longer, and they will be asked to return for a follow-up evaluation 10 to 14 days after study entry. Patients are to return for a further follow-up visit at 4 to 6 weeks (Day 28 to Day 42).

Patients who develop joint changes during therapy or during the follow-up period will be followed up for a further 3 months from the time of discharge. Any new objective finding noted on clinical joint or gait assessment will be thoroughly evaluated by the investigator. This evaluation may include diagnostic procedures, such as MRI and/or joint fluid assessments, as appropriate. Patients with joint changes during therapy, or during the follow-up period, should be followed up until:

- a) The adverse event has been resolved
or
- b) Until further change in the patient's condition is unlikely and a final causality assessment has been made. This may be shorter or longer than 3 months from the time of discharge.

A medical history will be obtained and thorough physical examination will be performed daily. Vital signs and intake/output records will be maintained for each 6-hour period from the time of administration of the first dose of the study drugs.

Patients will be closely monitored through bacteriological and laboratory assessments. Blood, urine and stool specimens will be taken at various time points. Stool culture for enteric pathogens will be done before initiation of the study drug, on study Day 3 and at follow-up visits. Rectal swab culture for *V. cholerae* will be done on each day of the study during the hospitalisation period, and at follow-up (10 to 14 days and 4 to 6 weeks). Complete blood count, serum electrolytes and creatinine, total bilirubin, SGPT and alkaline phosphatase will be determined before initiation of study drug and on study Day 5. (If the baseline creatinine is > 200 $\mu\text{mol/L}$, any patient with creatinine > than 200 $\mu\text{mol/L}$ 24-hour post-administration, will be considered as suffering from renal failure and will be withdrawn from the trial.) Urinalysis will be done before initiation of drug therapy, and on Day 5 of the study. Serum concentration of ciprofloxacin will be determined on the first day of the study at various time intervals after the first dose of the study drug has been administered.

Efficacy of the study drug will be assessed by clinical and bacteriological outcomes. For each patient, the study period will be divided into three phases as follows:

- Phase 1: Assessment of eligibility of enrolment in the study.
- Phase 2: Hospitalisation period (5 days or until resolution of diarrhoea whichever is longer). Study days will be counted from the time of administration of the first dose of the study drugs, and each 24-hour period will constitute a study day.
- Phase 3: Follow-up assessments: the interval between discharge of the patients from the hospital and the follow-up visits scheduled to occur 10 to 14 days after study entry, and 4 to 6 weeks after study entry.

5.2 Selection of subjects

5.2.1 Primary diagnosis

Cholera due to *V. cholerae* O1 or O139 of ≤ 24 hours duration.

5.2.2 Number of subjects

A total of 160 evaluable patients (patients who are infected with *V. cholerae* O1 or *V. cholerae* O139 and who will have completed 5 days of the study) will be required for this study.

5.2.3 Inclusion criteria

- Age: 2-15 years.
- Gender: Both.
- Duration of illness: ≤ 24 hours.
- Written informed consent for participation in the study from either of the parents, or guardian, and oral assent from children aged ≥ 8 years.

- Severe dehydration according to WHO guidelines (WHO guidelines filed in the investigator's file).
- Positive stool dark-field microscopic examination for *V. cholerae*.

5.2.4 Exclusion criteria

- History of receiving any antimicrobial agent (including study drugs) effective in the treatment of *V. cholerae* within 72 hours of screening.
- Concomitant infection(s) requiring antimicrobial therapy.
- A concomitant illness that may interfere with the evaluation of outcome or safety of the study drugs.
- Patients with known chronic renal insufficiency. [As all cholera patients with moderate to severe dehydration have pre-renal insufficiency on admission, and as it is not possible to detect whether a patient has renal failure until the patient has been hydrated for at least 24 hours, serum creatinine will be checked 24-hour post-administration of first dose of study medication, on Day 5, and at any time as clinically indicated. (If the baseline creatinine is > 200 mcmol/L, any patient with creatinine > than 200 mcmol/L 24-hour post-administration, will be considered as suffering from renal failure and will be withdrawn from the trial.)]
- Patients with known cardiac or hepatic impairment, i.e. SGOT/SGPT or bilirubin > 3 times the upper limit of normal, and patients with a history of central nervous system (CNS) disorders (known risk of experiencing seizures, a history of convulsive disorders or head injury trauma, currently on anti-seizure medication or within two months post-stroke).
- Patients previously enrolled in the study.
- Patients participating in any clinical study within one month prior to study entry.
- Patients known to have AIDS.
- Patients treated with quinolones in the 14 days prior to the study.
- Patients known to have underlying rheumatological disease, joint problems, etc.
- Patients with a known hypersensitivity to any of the study drug regimens or related compounds (including fluoroquinolones and macrolides).
- Female patients who are lactating, or are sexually active and using unreliable contraception.
- Patients having a known underlying rheumatological disease, joint problems secondary to trauma or pre-existing conditions known to be associated with arthropathy.
- Patients with conditions precluding the performance of a reliable series of musculoskeletal examinations are to be excluded from trial participation.

Note: Patients will be enrolled at any time of the day, and on any day of the year, subject to fulfilment of enrolment criteria.

5.3 Method of assigning subjects to trial groups and blinding procedure

Patients eligible for participation in this study will be randomly assigned to one of the two treatments.

"Code break cards" will be prepared, and will be retained by the investigator. Once, and only once a patient's eligibility for the study has been confirmed, the investigator will open the code break card with the lowest available number and allocate the patient to the treatment specified in the code break card.

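### Allocation concealment is not protected: the investigator keeps the code cards, and boxes labelled before supply carry both the regimen and the random number

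*Protocol*

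**What the plan says.** The only text on allocation is Protocol 5.3. The code break cards "will be prepared, and will be retained by the investigator". The timing rule is "Once, and only once a patient's eligibility for the study has been confirmed", after which "the investigator will open the code break card with the lowest available number and allocate the patient". The section does not name who confirms eligibility. It does not ask for sealed or opaque cards, a separate holder, or a record of each opening.

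Section 4.2 covers the drug boxes. "The labelling of ciprofloxacin suspension and erythromycin suspension will be done by Bayer Leverkusen", and "Each box will be clearly labelled with the following information". The list that follows includes a dosage line naming the drug (the erythromycin half runs "12.5 mg/kg 6 hourly for 3 days (erythromycin") and the random number. The patient's initials are the only item marked for completion by the investigator. The Research Officer keeps the supplies in a secure place and dispenses them.

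Section 4.1 shows that the contents differ: a single-dose ciprofloxacin suspension in one arm, and in the other "Two bottles of 100 ml (200 mg/5 ml) of active erythromycin suspension for doses 1 to 12". Section 5.1 states the design: "This is a randomised, open, parallel group clinical trial to compare the efficacy and safety". It places consent and random assignment after a 4-hour observation period in which stool output is measured.

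**The concern.** In an open trial, concealing the next assignment until a child is irrevocably enrolled is the main defence against selection bias. Here there are two ways in which it could become known early.

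The first is the cards. The role that keeps them is the role that opens them, and under section 7.2 it is also the investigators who explain the study to parents. Nothing physical or documentary enforces the timing rule.

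The second is the boxes. Cards are used in ascending order, so the next number is always known. If a box bearing that number also bears the regimen, the label discloses the arm without any card being touched.

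At the point of consent each child's purging rate is already known. Some criteria need judgement, such as a concomitant illness that may interfere with evaluation (5.2.4). The primary endpoint, cessation of watery stool within 48 hours without recurrence by Day 5, plausibly depends on initial severity. Selective approach could therefore carry through to the primary comparison, and no later analysis could reliably remove it.

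**Working it through.** **Side-by-side reading**

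1. Order of use: ascending, lowest available card next (5.3). The next number is known in advance.
2. Custody of cards: the investigator (5.3). Safeguard: open only after eligibility is confirmed. No sealing, opacity, separate holder or log is required.
3. Box label: applied by the sponsor and listing both regimen and random number (4.2). Only the initials are marked for the investigator to complete, so pre-printing of the random number is a fair inference.
4. Custody of boxes: the Research Officer (4.2).
5. From 1 and 3: if the box number equals the card number and each box bears only its own regimen, the lowest-numbered unused box shows the next arm. This route is open to whoever can see unused boxes. Sealing the cards does not close it.

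**The plan's own sample size, as background**

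Inputs from 9.1: rates 0.85 and 0.80, margin -0.15, two-sided 5% (one-sided 2.5%), power 90%. By the Farrington-Manning method:

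n = [(1.960 × s0 + 1.282 × s1) / (0.05 + 0.15)]²

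The restricted rates under the null are 0.7216 and 0.8716, so s0 = 0.5593. At the anticipated rates s1 = 0.5362. Then n = [(1.0963 + 0.6872) / 0.20]² = 79.5, so 80 per group, with power 90.2% at 80. Inflation for 10% invalidity: 80/0.9 = 88.9, so 89 per group and 178 in total, against 180 stated. These figures reproduce and are not in dispute.

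**Illustration of what a bias would do**

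The following inputs are assumptions and are not in the documents. Success is 90% in low-risk and 70% in high-risk children, and the arms differ by 15 to 25 percentage points in their share of low-risk children.

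Bias = imbalance × (0.90 − 0.70), so 0.15 × 0.20 = 3 points and 0.25 × 0.20 = 5 points.

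Take a true difference at the margin, 65% v 80%, with 80 per arm, and let the bias b raise the ciprofloxacin rate:

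Error = Φ(b/SE − 1.96), with SE taken at the shifted rates.

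| b | Rates | SE | b/SE | One-sided error |
|---|---|---|---|---|
| 0 | 0.65 v 0.80 | 0.0696 | 0 | 2.5% |
| +3 points | 0.68 v 0.80 | 0.0687 | 0.437 | 6.4% |
| +5 points | 0.70 v 0.80 | 0.0680 | 0.735 | 11.0% |

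Splitting the 5-point shift equally between the arms gives 10.6%, so the result depends little on that choice.

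The bias could equally run against ciprofloxacin. At the planned rates, a 5-point shift to 0.80 v 0.80 gives s0 = 0.5753 and s1 = 0.5657. Power is Φ[(0.15 × √80 − 1.960 × 0.5753) / 0.5657] = Φ(0.378) = 64.7%, down from 90.2%.

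**The case against.** The strongest reply is that the protocol already separates the two custodians and states the right order. The Research Officer holds the drug and the investigator holds the cards. To open a card implies that it was closed, and it may be opened only after eligibility is confirmed. Written consent is itself an inclusion criterion, and 5.1 places assignment after consent. Key entry conditions are measured: stool output of 20 ml/kg or more in 5.1 and positive dark-field microscopy in 5.2.3. All of this stands, and it narrows the room for selection. It does not close it. The timing rule is neither enforced nor recorded, the judgement criteria and the choice of whom to approach remain, and no text keeps enrolling staff from seeing unused boxes.

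A reader might infer that the next assignment is known with certainty, because one investigator confirms eligibility and allocates while numbered boxes stand on the ward. The documents do not support that. Section 5.3 does not say who confirms eligibility, and 4.2 does not place the boxes on the ward. It is nowhere stated that box and card numbers coincide or that the enroller sees boxes before enrolment. The investigator's initials entry shows handling of the box only once there is a patient. The joining word between the two dosage texts could even mean one common label, although the contents would still differ. The two-bottle erythromycin supply reveals the next arm only if packs are already tied to the sequence.

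A reader might also take the error rates as the expected bias. They show only what an assumed bias would do.

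**Conclusion.** The point holds as a lack of protection. The protocol does not show that the sequence will be disclosed or that enrolment will be selective. The weakness in card custody follows directly from 5.3. The weakness in the box labels rests on the natural but unstated reading that box and card numbers match, and on someone having access to the drug store before enrolment.

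The size of any bias cannot be derived from the documents. The rise in one-sided error from 2.5% to about 6.4% or 11% depends wholly on the assumed strata, imbalance and direction. Lack of blinding is a separate matter: the trial declares itself open, and this point concerns only what is known before a child is enrolled. Custody and labelling are fixed by the protocol itself, so they would not be left to a statistical analysis plan. This is a cheap improvement to make before drug is supplied.

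**What to change.** **Section 4.2.** Leave the random number off boxes that show the regimen, and write it on at dispensing, after allocation. Matched outer cartons showing only the number are a weaker option, because the contents differ visibly between arms.

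**Section 5.3.** Replace retention of the cards by the investigator with sequentially numbered, opaque, sealed envelopes, one series per hospital. They should be held by existing staff who take no part in screening, consent or enrolment. The Research Officer qualifies only if that condition is met. An envelope is opened only after patient identity, consent, eligibility, date and time have been written on it. Opened and unopened envelopes are reconciled at monitoring visits.

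**Cost.** A label change before supply, a set of envelopes, one rewritten paragraph and slightly slower dispensing. No change to sample size, analysis or treatment is needed, and no extra staff if an existing staff member meets the condition.

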5.4 Planned dosage and duration of treatment

5.4.1 Dosage and administration

Study drugs will be administered by a syringe without a needle to allow for precise dosing. If the child vomits within 30 minutes of administration of study drug, any other treatment may be given. Such patients will be valid for safety analysis, but invalid for the efficacy analysis.

Ciprofloxacin group

Ciprofloxacin will be administered orally in suspension formulation in a dose of 20 mg/kg body weight only once (maximum dose will be 750 mg).

Erythromycin group

Erythromycin will be administered in a dose of 12.5 mg/kg body weight every 6 hours for 3 days (maximum individual dose of 500 mg; total 12 doses).

5.4.2 Duration of treatment

Ciprofloxacin will be administered orally in suspension formulation in a dose of 20 mg/kg body weight only once (maximum dose will be 750 mg). Erythromycin will be administered in a dose of 12.5 mg/kg body weight every 6 hours for 3 days (maximum individual dose of 500 mg; total 12 doses).

5.5 Assessment periods

Efficacy of the study drug will be assessed by clinical and bacteriological outcomes. For each patient, the study period will be divided into three phases as follows:

- Phase 1: Assessment of eligibility of enrolment in the study.
- Phase 2: Hospitalisation period (5 days or until resolution of diarrhoea whichever is longer). Study days will be counted from the time of administration of the first dose of the study drugs, and each 24-hour period will constitute a study day.
- Phase 3: Post-therapy assessments: the interval between discharge of the patients from the hospital and the follow-up visits scheduled to occur 10 to 14 days after study entry, and 4 to 6 weeks after study entry.

5.6 Observations and measurements: assessment for treatment effects

5.6.1 Pre- and during treatment procedures

Only patients who fulfil the inclusion and exclusion criteria, and for whom informed consent has been obtained, will be eligible for enrolment into the study. At the time of enrolment into the study patients will be assessed for the following information, which will be recorded in the CRFs:

Medical history

Information obtained will include history of the current medical illness; current underlying/accompanying diseases; surgical procedures; current medication; previous joint problems and previous use of quinolones; and the date of onset of all underlying/accompanying diseases, if known, at screening.

Demographic details

At screening the following information will be recorded in the CRFs: sex, race and age.

Physical examination

Physical examination will be performed at screening, during the observation period: Day 1, Day 2, Day 3, Day 4, and Day 5; 10 to 14 days follow-up and 4-6 weeks follow-up. A physical examination will include the following:

- Height/length and weight.
- Temperature (axillary).
- Pulse/heart rate.
- Respiratory rate.
- Abdominal signs and symptoms.
- Determination of dehydration status, and rehydration and maintenance of hydration per World Health Organisation guidelines.

Examination of the joints

Clinical examination of joint function

As a part of the physical examination, the ankles, knees, hips, wrists, elbows and shoulders will be examined for pain and tenderness, evidence of inflammation (redness, warmth, and swelling will lead to the exclusion of the patient) and active/passive range of motion. Other symptomatic joints will be examined as well.

Joint examinations will be performed as follows: before initiation of drug therapy daily during hospitalisation; at follow-up 10 to 14 days after study entry; and at 4 to 6 weeks after study entry. Children who develop a joint problem during therapy, or during the follow-up period, should be followed up until:

- (a) The adverse event has resolved
or
- (b) Until a further change in the patient's condition is unlikely and a final causality assessment has been made. This may be shorter or longer than 3 months from the time of discharge. All efforts will be made to examine the joints during and after completion by the same investigator. All findings will be recorded in the CRFs.

Laboratory assessments

- **Faecal cultures:** stool culture for enteric pathogens (*V.cholerae*, *Salmonella*, *Shigella* and *Campylobacter*) will be done before initiation of the study drug, Day 3 and *Salmonella*, *Shigella* and *Campylobacter* cultures will be done on patients who are symptomatic at the follow-up visits. A rectal swab will be done for isolation of *V. cholerae* O1 and O139 at baseline i.e. on the day of admission and before initiation of the study drug, on each day of hospitalisation, at the time of first follow up visit (10 to 14 days) and at 4 to 6 weeks follow-up.

- **Determination of antimicrobial susceptibility:** this will be done for *V. cholerae* and other enteric pathogens isolated from the specimens collected before initiation of drug therapy. Susceptibility to tetracycline, trimethoprim-sulfamethoxazole, chloramphenicol, erythromycin, furazolidone and ciprofloxacin will be done using the disc-diffusion method. In addition, the minimum inhibitory concentration (MIC) and susceptibility of the study isolates to only ciprofloxacin will be determined by E-test.
- **Microscopic examination of stool:** this will be done before initiation of study drugs and on study Day 4 for semi-quantitative assessment of presence of leukocytes and erythrocytes, as well as demonstration of haematophagous trophozoites of *E. histolytica* and other parasites and their ova.
- **Blood culture:** this will be done only when clinically indicated.
- **Haematology:** haematocrit, total and differential (neutrophils, lymphocytes, monocytes, eosinophils, basophils) white blood cell counts, and platelet count will be done before initiation of the study medication on the day of admission (pre-therapy) and on study Day 5 (post-therapy). This will require drawing of about 0.5 ml of blood from a vein in the elbow of the patients.
- **Blood chemistry:** serum sodium, chloride, potassium, bicarbonate, creatinine, bilirubin, AST, ALT and alkaline phosphatase will be performed before initiation of the study drugs (pre-therapy) on the day of admission and on study Day 5 (post-therapy). This will require collection of about 4.0 ml of blood from a vein in the elbow of the patients on each of these occasions.
- **Pharmacokinetics:** ciprofloxacin concentrations will be determined for both stool and serum.
 - To determine the pharmacokinetics of ciprofloxacin, blood samples will be taken from each patient during one of four time periods; before drug administration; within 1 hour of first drug administration; 1-2 hours after first drug administration; and 4-12 hours after the first dose. A 3-ml blood sample (sufficient to yield 1 ml of plasma) will be drawn at each collection time.
 - Stool will be collected 6-hourly for the first 72 hours of the study (thus 12 stool samples per patient).
 - Concentrations will be determined using the HPLC-method. Concentrations will be determined on both uncentrifuged and centrifuged supernatant samples, to determine how much of the drug is protein bound.
 - Erythromycin concentrations will be determined only in stool, which is the active site of infection.

The analysis will be conducted by [name], Bayer. Samples will be transported to the Bayer laboratory in Germany.

Instructions for transporting ciprofloxacin blood samples for the PK evaluation are as follows:

- Protect samples during all steps from direct sunlight.
- Blood samples should be drawn into NH₄-heparin tubes.
- Blood, adequate to produce 1 ml of plasma should be drawn at each sampling time (e.g. a 3-ml blood sample, sufficient to yield 1 ml of plasma).
- Up to 2 hours after sampling, the blood should be centrifuged for 10 minutes at 2000 g and +20°C. The plasma must then be separated and transferred into appropriately labelled tubes (glass, polystyrene, or polypropylene).
- Samples should be stored at about -20°C and shipped on dry ice.
- Analyses must be performed within 24 months.

- **Urinalysis:** urine specimen will be tested for pH, protein, ketones, blood and glucose. General appearance will be determined, and microscopic examinations will be done for cells, casts and crystals. This will be done before initiation of the study drugs on the day of admission and on Day 5. Any casts or crystals will be described in detail.

Note: A flow chart of required tests and observations is presented in Appendix 12.1.1 and a clinical examination of joint functions is presented in Appendix 12.1.2.

Case Management

Clinical evaluation and laboratory studies

Patients will be hospitalised for at least 5 days. The following clinical evaluations will be performed on study patients:

- **Weighing:** before rehydration (dehydrated weight), after rehydration (rehydration weight) and just before administration of the study drug (after the 4-hour observation period; rehydration weight -2), and at 24 hour intervals from the time of administration of the first dose of the study drug during hospitalisation. An electronic weighing scale (Sartorius, accuracy 10 grams) will be used for this purpose.
- **Physical examination:** before rehydration, after rehydration, at the time of administration of the study drug, and then daily during hospitalisation. In addition to evaluation of hydration status, the history and physical examinations will also focus on adverse events including vomiting, gastrointestinal distress, rash, and joint assessment.
- **Vital signs:** axillary temperature, pulse and respiratory rates, and blood pressure will be recorded before rehydration, after rehydration, just before administration of study drug, and then every 6 hours during the study.
- **Quantitation of stool, urine and vomit volume:** this will be done for the rehydration and the observation periods, and then for each 6 hour period during the study.
- **Rehydration guidelines:** children admitted with severe dehydration according to the WHO guidelines will be given 100 ml/kg of Dhaka Solution over 3-4 hours. After initial rehydration, children will be evaluated and appropriate treatment plan will be used for continuation of further fluid therapy. Fluids given to maintain hydration should be based on the amount of ongoing stool losses as well as the child's willingness to drink. Fluid therapy will continue until diarrhoea stops. If signs of dehydration reappear, fluid appropriate to the degree of dehydration will be administered and the study protocol will continue to be followed.
- **Feeding:** appropriate feeds for age will be provided.
- **Procedures to be followed in the case of pathological changes of the joint:** a radiological examination of the affected joint and the contra-lateral joint (i.e. normal joint opposite the affected joint) will be performed. Efforts will also be made to perform ultrasonographic and magnetic resonance imaging (MRI) examination of the affected and the contra-lateral joints and/or joint fluid assessments, as appropriate.

Laboratory evaluation

For evaluation of bacteriologic response to the treatment regimen, stool or rectal swab culture will be done on each day of the study for isolation and identification of *V cholerae* O1 or O139. Stool culture for enteric pathogens will be done before initiation of study drug, on Day 3 and follow-up visits.

Reporting treatment failures

If the study treatment is judged to have clinically failed, patients will be treated at the investigator's discretion.

